### 6.11.2 Sensitivity Analysis of the First Co-Primary Endpoint

Sensitivity analysis may be carried out using the CMH test stratified by the randomization stratification factors (baseline DSQ and age) to assess robustness of Fisher’s exact test results.

A sample SAS code for the pairwise comparison is as follows.

```

* COMPUTES CMH P-VALUE AND NEWCOMBE COMMON RISK DIFFERENCE ;
ods output CMH=PVAL(where=(althisypothesis='Row Mean Scores Differ'))
CommonPdiff=DIFF;
proc freq data=ADEF ;
    tables DSQ_Strata*AGE_STRAT*TRTP*RESP / cmh commonriskdiff
    (cl=NEWCOMBE) ;
run ;

```

The rationale for specifying Fisher’s exact test as the primary analysis as opposed to specifying the CMH test is because when a stratum has 100% response for 1 treatment group and 0% response for another treatment group, the CMH test may lose efficiency or not be computable. This is evident from the Phase 2 study outcome.

### 6.11.3 Subgroup Analysis of the First Co-Primary Endpoint

Analysis comparing AK002 and placebo will use Fisher’s exact test for each of the subgroups defined in Section 5.9.

### 6.11.4 Analysis of the Second Co-Primary Endpoint

The second co-primary endpoint will be analyzed by ANCOVA (primary analysis) using the imputed data set (Section 5.4.2). The LSM, SE, and 95% CI for each treatment group and for the between group difference will be derived from ANCOVA with treatment as a factor, baseline DSQ and age as covariates. The hypothesis test for the treatment effect will be carried out by the F-test. The synthesizing method will be used to combine the results from multiple imputations.

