### 3.6 Determination of Sample Size

To achieve statistical significance for the first co-primary endpoint, a sample size of 8 subjects per treatment group will provide 90% power to demonstrate a statistically significant difference between AK002 and placebo in achieving the histological response (defined as the peak esophageal intraepithelial eosinophil count  $\leq 6$  cells/hpf) at Week 24. This calculation is based on the AK002-003 study in which 90% of AK002 subjects and 10% of placebo subjects achieved the histologic response at Day 99. The hypothesized treatment effect of 80% yielded a small number of subjects per group for the first co-primary endpoint.

To achieve statistical significance for the second co-primary endpoint, a sample size of 86 subjects per treatment group will provide 90% power to demonstrate a statistically significant difference between any AK002 dose group and placebo treatment group in mean absolute change in DSQ score from baseline to Weeks 23–24. This calculation is based on the baseline score of  $30 \pm 15$  (mean  $\pm$  Standard Deviation [SD]) reported in the literature, and an expected mean reduction of 15 in the AK002 group and 7.5 in the placebo group, and a SD of 15 for the change from baseline (Dellon, 2021; Hirano, 2019; Hudgens, 2017).

Consequently, approximately 100 subjects per treatment group will be included for a total of 300 subjects, driven by the second co-primary endpoint and a potential 14% dropout rate.

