#### 5.4.2 Missing Daily PRO Scores at Weeks 23–24

The PRO daily scores will be set to missing if they are collected after subjects have experienced an ICE. For the endpoint of change in the biweekly DSQ score, the biweekly average score will be calculated using the available daily scores. The validated DSQ calculation normalizes the missing daily scores within the 14-day, biweekly interval.

Missing DSQ scores during Weeks 23–24 will be imputed using the MCMC method. Baseline tissue eosinophil count and baseline DSQ and age strata will be included along with the average biweekly DSQ (W01\_02, W03\_04, W05\_06, ..., W21\_22, W23\_24) in the multivariate distribution construction. The imputation will be carried out for each treatment group separately and will be executed multiple (50) times (MI). The purpose of MI is to account for the imputation variability in the parameter estimates. Missing data imputation (PROC MI) will be conducted separately for active AK002 treatment groups. An example of the SAS code for this imputation follows.

```
proc mi data=DSQ seed=1357986420 nimpute=50
  out=DSQ_IMPUTED ;
  by TRTMT ;
  class AGE_STRATA;
  mcmc chain=multiple impute=full initial=em nbiter=200 niter=100 ;
var B_EOS B_DSQ DSQ_W01_02 DSQ_W03_04
... DSQ_W21_22 DSQ_W23_24 ;
run ;
```

After imputation, the LSM and SE are derived from the conventional ANCOVA from each imputed data set. These LSM and SE are synthesized to derive the imputation variability-adjusted LSM and SE for each treatment group and for the between treatment difference.

These synthesized LSM and SE are then used in the hypothesis test for the between treatment difference. An example of the SAS code for the synthesized LSM comparisons between treatment is as follows.

```
ods output ParameterEstimates=LSMDIF ;
proc mianalyze data=LSMDIFF alpha=0.05 ;
  by trtmt;
  modeleffects LSM ;
  stderr SE ;
run ;
```

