## 5.8 Multiple Comparisons/Multiplicity Adjustment

A hierarchical procedure will be used to control the overall Type I error rate at 0.05 for the primary endpoint and the secondary endpoints across the 2 AK002 dose regimens vs. placebo. Each hypothesis will be formally tested only if the preceding hypothesis is significant at the 2-sided 0.05 significance level. The hierarchical testing order (all comparisons are with the placebo) is as follow:

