**Table 7 Hypothesis Testing Order Hierarchy**

Endpoint Description	AK002 IV Dose Groups	
	Low Dose	High Dose
Primary Endpoints		
1) The proportion of subjects who achieve a peak esophageal intraepithelial count of $\leq 6$ eosinophils/hpf at Week 24.	8	1
2) Mean change in DSQ score from Baseline to Weeks 23–24.		
Secondary Endpoints		
1) Percent change in peak esophageal intraepithelial eosinophil count at Week 24.	14	7
2) Proportion of subjects achieving peak esophageal intraepithelial eosinophil count of $\leq 1$ eosinophil/hpf at Week 24.	9	2
3) Proportion of subjects achieving peak esophageal intraepithelial eosinophil count of $< 15$ eosinophils/hpf at Week 24.	18	17
4) Proportion of treatment responders when a responder is a subject achieving $> 30\%$ reduction in symptoms (DSQ) at Weeks 23–24 and achieving a peak intraepithelial eosinophilic count of $\leq 6$ eosinophils/hpf at Week 24.	10	3
5) Proportion of subjects with $> 50\%$ reduction in DSQ score from Baseline to Weeks 23–24.	12	5
6) Percent change in DSQ score from Baseline to Weeks 23–24.	11	4
7) Change in biweekly mean DSQ over time.	16	15
8) Change in EoE Endoscopic Reference Score from Baseline to Week 24.	13	6

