#### **6.11.1 Analysis of the First Co-Primary Endpoint**

The first co-primary endpoint will be analyzed using the imputed data set (Section 5.4.1). Fisher's exact test (primary analysis) will be conducted comparing AK002 with placebo for the proportion of tissue eosinophil responders. Proportion of responders and the associated 95% CI will be presented for each treatment group. The between group difference (pairwise comparison with placebo) and the associated 95% CI will also be computed and presented. A sample SAS code is as follows.

```

* COMPUTE 95% EXACT CONFIDENCE INTERVAL FOR %RESPONSE FOR INDIVIDUAL
TREATMENT ;
ods output BinomialCLs=CL ;
proc freq data=ADEF ;
    table RESP / out=CNTS bin(cl=midp) ;
    by TRTAN ;
run;

* COMPUTE 95% EXACT CONFIDENCE INTERVAL AND FISHERS EXACT P-VALUE FOR
BETWEEN TREATMENT DIFFERENCE ;
ods output FishersExact=PVAL(where=(name1='XP2_FISH'))
RiskDiffCol2=DIFF(where=(row='Difference')) ;
proc freq data=ADEF ;
    table TRTPN*RESP / riskdiff(cl=exact) exact ;
run ;

```

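### SAP 6.11.4 names an F-test that does not fit Table 7's separate dose-versus-placebo steps, and the Appendix 4 example code pools the dose differences together and leaves out age

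*SAP*

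**What the plan says.** SAP 6.11.4 analyses the change in DSQ by ANCOVA on the imputed data, with treatment as a factor and baseline DSQ and age as covariates. It then states: "The hypothesis test for the treatment effect will be carried out by the F-test". It names no contrast, no degrees of freedom and no two-arm subset.

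SAP 5.8 sets a fixed sequence in which every comparison is with placebo: "Each hypothesis will be formally tested only if the preceding hypothesis is significant at the 2-sided 0.05 significance level". Table 7 puts the co-primary endpoints at step 1 for the high dose and step 8 for the low dose. Percent change in DSQ is at steps 4 and 11, and 6.12.5 refers its method back to 6.11.4.

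SAP 5.4.2 describes the test differently: "These synthesized LSM and SE are then used in the hypothesis test for the between treatment difference". On the imputation model it says: "Baseline tissue eosinophil count and baseline DSQ and age strata will be included along with the average biweekly DSQ". The variable list in its code begins "var B_EOS B_DSQ DSQ_W01_02 DSQ_W03_04" and contains only baseline eosinophils, baseline DSQ and the biweekly DSQ scores. `AGE_STRATA` appears in the CLASS statement only.

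SAP 9.4 (Appendix 4) gives example code for the whole chain. Its ANCOVA model has `DISEASE_STRAT`, baseline DSQ and treatment. It asks for all pairwise treatment differences, gives every one the label `DIFF`, and pools by that label.

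**The concern.** With treatment as a three-level factor, the ordinary meaning of an F-test for the treatment effect is a 2-df test that all three means are equal. It yields one p-value. Table 7 needs two, seven steps apart, and step 1 gates every later test. Used literally, the same p-value would serve as the DSQ part of both step 1 and step 8.

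A programmer who turned to Appendix 4 to settle the matter would not find the answer. Without an arm restriction, that code merges the two contrasts of interest with a third one, high dose against low dose, that no hypothesis uses. It also fits a model that differs from the one in 6.11.4. This is the endpoint that sized the trial, so its test should have one reading, and the example code should match it, before the blind is broken.

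**Working it through.** **1. The plan's own figure.** Inputs from SAP 3.6: expected reductions of 15 and 7.5, so a difference of 7.5; SD 15; 90% power. Two-sided 0.05 is from SAP 5.8.
- At 86 per arm the SE of a difference is √(2 × 15² / 86) = 2.29, and 7.5 / 2.29 = 3.28.
- The noncentral t (two-arm error df) gives 90.3% power at 86 and 89.99% at 85, so 86 reproduces.
- 86 / (1 − 0.14) = 100 per arm.

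The trial was therefore sized for a pairwise test, as the text says: "statistically significant difference between any AK002 dose group and placebo treatment group in mean absolute change in DSQ score".

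**2. The texts side by side.**
- 6.11.4: F-test of the treatment effect, contrast not named.
- 5.4.2: pools one estimate with one SE, then tests a between-treatment difference. That is a one-parameter test.
- 5.8 and Table 7: each dose against placebo, at its own step.
- 6.11.1, for the first co-primary endpoint: "The between group difference (pairwise comparison with placebo) and the associated 95% CI will also be computed and presented".
- 6.12.6, for DSQ over time: the group difference is defined as active dose against placebo, by a simple contrast.

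Four places point to a dose-versus-placebo contrast. Only 6.11.4 can be read otherwise.

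**3. Appendix 4 run on all three arms.** Assumptions: planned effects (mean change −7.5 on placebo, −15 on each dose), SD 15, 100 per arm, placebo sorted first, no covariate gain and no missing-data variance. The three differences are placebo − low = 7.5, placebo − high = 7.5 and low − high = 0. Over 50 imputations, 150 values share the label `DIFF`, and Rubin's rules give:
- Pooled estimate: (7.5 + 7.5 + 0) / 3 = 5.0
- Within-variance: 2 × 225 / 100 = 4.5
- Between-variance: 50 × (2.5² + 2.5² + 5²) / 149 = 1875 / 149 = 12.58
- Total variance: 4.5 + (1 + 1/150) × 12.58 = 17.17, so SE = 4.14
- t = 5.0 / 4.14 = 1.21, p = 0.23

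The high-dose contrast alone is 7.5 with SE √4.5 = 2.12, t = 3.54, p = 0.0005.

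**4. Dependence on sort order.** For arms sorted a, b, c, the mean of a − b, a − c and b − c is (2/3)(a − c). With placebo first this is (2/3) × 7.5 = 5.0. With placebo in the middle it is (2/3) × (one dose − the other) = 0 at equal dose effects. The size of the error depends on the coding of the arms. The mixing of contrasts does not.

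**5. Age.** 6.11.4 adjusts for age, but the Appendix 4 model has no age term. `DISEASE_STRAT` is defined nowhere in the SAP, and the randomization strata are age and baseline DSQ (Protocol 10.2). The 5.4.2 text puts age strata in the imputation, while its VAR list does not.

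**6. Under the intended test.** The 1-df contrast from a three-arm model has 90.4% power at 86 per arm and 94.1% at 100. Two separate two-arm models give 90.3% at 86.

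**The case against.** The best defence is that the SAP, read as a whole, already settles the test. Section 5.8 fixes placebo as the comparator, 4.2.6 defines the summary as the difference between AK002 and placebo least squares means, 5.4.2 pools a single parameter, and a 1-df F is simply t squared. The SAP gives no procedure for pooling a 2-df F over 50 imputations. All of this stands, and it is why the F-test sentence is an inconsistency and not a wrong analysis waiting to happen.

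Appendix 4 is also labelled an example and is visibly unfinished: it saves one dataset name and reads another, and the STDERR statement in the pooling step names no variable. On a two-arm subset there is one difference per imputation and nothing is mixed. SAP 7 requires independent reprogramming. These points limit the harm. But no subset is stated, and second programming confirms that two programs agree, not that the specification is right.

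A reader might go further and infer that the plan loses power, or that step 1 could be passed on the low dose alone. The documents do not support either reading. Both rest on an overall test that the SAP does not say how to pool. At the planned effects an overall F would have more power than the contrast (93.1% against 90.4% at 86 per arm). A loss appears only if the low dose is assumed weaker, and the dose ratio available for that comes from a different symptom score in a different disease (the Phase 2 study in gastritis and duodenitis, Protocol Synopsis). Step 1 also requires the high dose to succeed on histology by its own comparison with placebo.

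**Conclusion.** The point holds as an inconsistency that should be fixed before unblinding. Read literally, the F-test sentence in 6.11.4 cannot deliver steps 1 and 8 of Table 7, or steps 4 and 11 through 6.12.5, although the intended contrast is clear from elsewhere in the SAP. The firmer error is Appendix 4. If run on all arms it would turn a result of p=0.0005 into p=0.23 in the illustration, or into an estimate of zero under another arm order. In any form it omits the age term that the primary model requires. Those figures assume the planned effects, 100 per arm and no missing-data variance, and they arise only if no two-arm subset is taken. No size is claimed for the age omission. The sample size of 86 per arm, about 100 with dropout, is unaffected.

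**What to change.** - **6.11.4:** replace the F-test sentence with the MI-combined, two-sided, 1-df ANCOVA contrast of each dose minus placebo, tested at its Table 7 step. Section 6.12.5 then follows it.
- **9.4, contrasts:** keep only the two active-minus-placebo differences, label them separately (for example `DIFF_HIGH` and `DIFF_LOW`) and pool by that label. Correct the dataset name and the empty STDERR statement at the same time.
- **9.4, model:** replace `DISEASE_STRAT` with the age stratum.
- **5.4.2 and 9.4, imputation:** add age to the VAR lists as a numeric 0/1 indicator.

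Whether one three-arm model or two two-arm models are fitted is a matter of preference, given the near-identical power, but the SAP should say which. The cost is a few lines of text and example code before unblinding, with no change to design, estimand, alpha or sample size.

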### 6.11.5 Sensitivity Analyses of the Second Co-Primary Endpoint

The 2 sensitivity analyses planned below are constructed based on the already imputed bi-weekly data set from Section 5.4.2. From this imputed data set, the bi-weekly DSQ is set to missing if it is derived from the daily scores collected on/after ICE event. This setting creates the monotone missing data set.

The first sensitivity analysis is based on the placebo-based pattern-mixture model for the missing data imputation under the missing not at random (MNAR) assumption. In this model, subjects from the active treatment group after the ICE are assumed to behave like the subjects from the placebo group. Their missing data are imputed using the response profile from the placebo subjects who have similar baseline covariates and prior response trajectory. The sample SAS code follows.

```
proc mi seed=135791 nimpute=10;
  class TRTMT;
  var B_EOS Age_Grp B_DSQ DSQ_W01_02 DSQ_W03_04 ... DSQ_W21_22
      DSQ_W23_24;
  monotone reg;
  mnar model(DSQ_W01_02 DSQ_W03_04 ... DSQ_W21_22 DSQ_W23_24 /
    modelobs=(TRTMT='0')); * CODE 0 IS FOR PLACEBO GROUP ;
run ;
```

The second sensitivity analysis is based on the tipping point method. In this method, the missing biweekly DSQ will be imputed with different adjustments for the active treatment subjects and placebo subjects under the MNAR assumption in which the search for a tipping point reverses the study conclusion (i.e., p-value no longer <0.05 for the treatment effect). A shift ranging from -x to +y representing different level of improvement or worsening due to ICE will be added to the imputed DSQ. An example of the SAS code follows.

```
proc mi seed=579864 nimpute=10;
  class AGE_STRAT TRTMT;
  var B_EOS B_DSQ DSQ_W01_02 DSQ_W03_04 ... DSQ_W21_22 DSQ_W23_24;
  monotone reg;
  mnar adjust(DSQ_W01_02 / adjustobs=(TRTMT='1') shift=&d1.)
    adjust(DSQ_W03_04 / adjustobs=(TRTMT='1') shift=&d1.)
    . . .
    adjust(DSQ_W21_22 / adjustobs=(TRTMT='1') shift=&d1.)
    adjust(DSQ_W23_24 / adjustobs=(TRTMT='1') shift=&d1.)
    adjust(DSQ_W01_02 / adjustobs=(TRTMT='0') shift=&d0.)
    adjust(DSQ_W03_04 / adjustobs=(TRTMT='0') shift=&d0.)
    . . .
    adjust(DSQ_W21_22 / adjustobs=(TRTMT='0') shift=&d0.)
    adjust(DSQ_W23_24 / adjustobs=(TRTMT='0') shift=&d0.);
run;
```

**Note:** A positive adjustment (shift>0) will increase (worsen) the DSQ score and a negative adjustment (shift<0) will reduce (improve) the DSQ score. Varying shift parameter from 0 (minimum) to maximum, where maximum shift parameter will be guided by the mean difference between subjects that drop out after the tth visit and subjects that continue. This sensitivity analysis will vary the shift parameter independently between the active treatment subjects and placebo subjects.

After the data are imputed, the ANCOVA with the synthesizing method will be applied using methods described in Section 5.4.2.

P-values for the between treatment comparison from the synthesized ANCOVA results will be plotted against the shift parameters to demonstrate the robustness of the study conclusion against the various imputation strategies to account for the ICE effect.

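### SAP 6.11.5 does not say how the 50 existing and 10 new imputations are combined in the two MNAR analyses, and its tipping-point call leaves treatment out of the imputation model

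*SAP*

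**What the plan says.** SAP 5.4.2 imputes missing biweekly DSQ scores separately for each treatment group, 50 times, runs the ANCOVA on each completed set and combines the results. Appendix 4 codes the ANCOVA by `_imputation_`.

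SAP 6.11.5 describes the placebo-based pattern-mixture analysis and the tipping-point analysis as "constructed based on the already imputed bi-weekly data set from Section 5.4.2". Scores from the intercurrent event (ICE) onward are reset to missing, which leaves a monotone pattern, and PROC MI is run again. The tipping-point call opens with "proc mi seed=579864 nimpute=10", and the placebo-based call also uses `nimpute=10`. Neither call has `DATA=`, `OUT=` or `BY _Imputation_`. The tipping-point call has the statement "class AGE_STRAT TRTMT", but its VAR list holds only baseline eosinophils, baseline DSQ and the biweekly scores, and there is no `BY TRTMT`. Its shifts are coded for `TRTMT='1'` and `TRTMT='0'`.

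On the next step, SAP 6.11.5 says only: "After the data are imputed, the ANCOVA with the synthesizing method will be applied using methods described in Section 5.4.2". Both code blocks are introduced as samples or examples.

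**The concern.** There are three gaps, and they should be kept apart.

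1. **Combining.** The input already contains 50 versions of each subject. If a new PROC MI is run across all of them, each new data set holds 50 rows per subject, and the imputation regressions and the ANCOVA take those rows for people.
2. **Treatment omitted, tipping-point call only.** Missing scores are drawn from regressions pooled over the arms, whereas 5.4.2 imputes by arm. Zero shift should return the primary result, and here it would not.
3. **Shift codes.** There are two doses and placebo but two shift codes, and the SAP does not say whether the call is run once or once per dose.

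These are the only planned MNAR checks on the symptom co-primary. They feed Tables 14.2.2.2 and 14.2.2.3 and Figure 14.2.2. An error in the first item would make a fragile result look secure.

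**Working it through.** **Inputs from the SAP.** Section 3.6: "an expected mean reduction of 15 in the AK002 group and 7.5 in the placebo group", a difference of 7.5; "a SD of 15 for the change from baseline"; 14% dropout. Section 5.8: "Each hypothesis will be formally tested only if the preceding hypothesis is significant at the 2-sided 0.05 significance level". Section 3.3.3: three arms, 1:1:1, about 300 subjects. Section 5.4.2: 50 imputations by arm.

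**Assumptions not in the documents.** The correlation of repeated DSQ scores, uniform dropout timing, no intermittent gaps (so the 50 copies are identical before re-imputation), 10% adolescents, and shifted values carrying into later visits. Dropout of 7% and 25% is a range around the stated 14%.

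**Step 1. The plan's own figure.** The SAP states that "a sample size of 86 subjects per treatment group will provide 90% power".
- Normal approximation: n = 2(1.960 + 1.282)² × 15² / 7.5² = 84.1, so 85.
- Noncentral t: power 0.8999 at 85 and 0.9032 at 86, so 86 reproduces.
- Dropout: 86 / 0.86 = 100 per arm.

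The SAP gives no standard error or tipping point for the MNAR analyses. For scale, the unadjusted SE with 100 per arm is 15 × √(2/100) = 2.12.

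**Step 2. Stacking, if the sets are not separated.**
- Rows: 50 × 300 = 15,000.
- SE factor: 1/√50 = 0.141, so 2.12 × 0.141 = 0.30.
- Under no effect, a nominal two-sided 5% test would reject with probability 2Φ(−1.96 × 0.141) = 2Φ(−0.277) ≈ 0.78.

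Simulated SE of one dose's difference from placebo, placebo-based analysis, 100 per arm:

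| Dropout | 50 sets kept separate, one draw each | 50 sets stacked, 10 draws | Ratio |
|---|---|---|---|
| 7% | 2.197 | 0.306 | 7.2 |
| 14% | 2.248 | 0.308 | 7.3 |
| 25% | 2.404 | 0.323 | 7.4 |

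**Step 3. Treatment omitted from the tipping-point model, zero shift, no stacking.**

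| Dropout | Imputed by arm (SE) | Pooled over arms (SE) | Pull toward no effect |
|---|---|---|---|
| 7% | −7.702 (2.199) | −7.507 (2.189) | 0.195 / 7.702 = 2.5% |
| 14% | −7.489 (2.264) | −7.027 (2.215) | 0.462 / 7.489 = 6.2% |
| 25% | −7.492 (2.430) | −6.683 (2.327) | 0.809 / 7.492 = 10.8% |

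The other simulated dose gave 2.9%, 5.7% and 10.9%. A second simulation (150 trials, AR(1) correlation 0.8, 14% dropout) gave −7.4 (SE 2.35) by arm and −6.7 (SE 2.30) pooled, a pull of 0.7 / 7.4 = 9.5%. The SE hardly moves in either.

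**Step 4. Effect on the tipping point.** The median shift needed to lose significance, for one dose against placebo with both doses shifted at 14% dropout, was:
- 5.9 with treatment as a model term;
- 4.7 with treatment omitted;
- 12.9 with treatment omitted and the sets stacked.

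These are medians of 14 simulated trials and show direction and rough size only.

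**Step 5. Three arms in one run, second dose coded separately.** In one simulated trial, raising the shift on arm `'1'` from 0 to 10 took that arm's p-value from 0.0006 to 0.30. The other dose's difference went from −8.47 to −8.52 (p from 0.0002 to 0.0008). The unshifted dose is not tested.

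**The case against.** The strongest reply is that this is abbreviated example code. The calls name no input and no output and contain ellipses. Other blocks are plainly templates: Appendix 4 uses a disease stratum that this trial does not have. A reader might infer that the planned standard errors and tipping point *are* wrong. The documents do not support that. They leave the step unspecified, and the 7-fold error arises only if someone stacks the sets.

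Section 6.11.5 also refers back to an ANCOVA on each imputed set. That helps only if the index used is the one that separates the 50 existing sets. An ANCOVA run by the 10 new imputations would still see 50 rows per subject.

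A reader might also infer that one dose is never shifted. That is not established. The text speaks of active subjects in general, each dose is compared with placebo separately in Table 7, and two codes are right if the call is run per dose.

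Nor does omitting treatment make results look robust. It pulls the estimate toward no effect and brings the tipping point earlier. It does not touch the placebo-based call, which is fitted on placebo subjects and needs no treatment term.

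Finally, an SE near 0.3 beside a primary SE near 2.3 would be conspicuous, and the DSQ responder endpoints count subjects with an ICE as non-responders, which gives a view of symptoms that does not rely on missing-at-random imputation.

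All of this limits the point without removing it. Section 6.11.5 is the only specification of these analyses. The SAP writes its BY statements elsewhere where it wants them. Section 7 validates tables by independent reprogramming until results match, and two programmers following the same code would agree with each other.

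**Conclusion.** The point holds in conditional form. The SAP does not state how 50 existing and 10 new imputations are combined. Followed as printed on stacked data, both MNAR analyses would have SEs about 7 times too small. That factor is essentially √50 and barely depends on dropout.

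The omission of treatment is a separate and smaller fault, confined to the tipping-point call. It shifts the zero-shift reference toward no effect by about 6–10% at 14% dropout, and about 3–11% over 7–25%, with little change in SE. These percentages rest on assumed correlations and monotone dropout. All of the SE error comes from stacking.

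The per-dose question is an ambiguity to settle, and it disappears if the call is run for each dose against placebo. The primary DSQ analysis is not affected. The SAP should be corrected before unblinding.

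**What to change.** - State that, within each of the 50 sets from 5.4.2, scores on or after the ICE are reset to missing. Then run PROC MI `BY _Imputation_` with `nimpute=1`, run the ANCOVA by `_Imputation_`, and combine the 50 results. If 10 draws per set are kept, state a nested combining rule instead.
- Name the input and output data sets in both calls.
- In the tipping-point call, add TRTMT to VAR or impute by arm, and check that zero shift agrees with the primary analysis up to simulation error.
- State that the tipping-point call is run separately for each dose against placebo, with the dose under test being the one shifted.

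The cost is SAP wording and code. Trial conduct, sample size and the primary analysis do not change.

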8.1 Prohibited Medications

Any biologics or medications that may interfere with the study, such as swallowed corticosteroids, systemic corticosteroids, and systemic immunosuppressive or immunomodulatory drugs (including azathioprine, JAK inhibitors, 6-mercaptopurine, methotrexate, cyclosporine, tacrolimus, anti-TNF, anti-IL-4 receptor (e.g., dupilumab), anti-IL-5 (e.g., mepolizumab), anti-IL-5 receptor (e.g., benralizumab), anti-IL-13 (e.g., lebrikizumab), anti-IgE (e.g., omalizumab), are prohibited for the duration of study participation.

The use of systemic or topical corticosteroids with a dose of >10 mg/day of prednisone or equivalent is prohibited unless it is due to unforeseen circumstances when it is deemed to be medically necessary to treat an unrelated medical condition or when given as a premedication prior to infusion or to treat an IRR that occurs during infusion. Any medications used for the treatment of IRR are not considered deviations from the protocol.

Subjects will be reminded to not take prohibited medications and to notify the site immediately if a prohibited medication is prescribed by another health care provider.

If medically necessary, rescue medications (systemic and/or swallowed topical corticosteroids) or emergency esophageal dilation may be used as rescue therapy. Any subject requiring rescue therapy must have an EGD (with biopsy collection and EREFS scoring) done prior to initiation

of rescue medications (or at the time of emergency esophageal dilation). The EGD performed due to initiation of rescue therapy will be used in place of the EGD scheduled for Day 169 (Week 24), and the subject will not have an EGD performed at the Day 169 (Week 24) visit. Subjects receiving rescue therapy should remain blinded, continue to receive study drug, and continue to comply with all study visits and assessments in accordance with the Schedule of Events (Table 1).

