#### **4.2.4 Intercurrent Events**

The events below are considered intercurrent events (ICE) confounding with the efficacy outcomes.

- Premature discontinuation from the study
- Use of prohibited/rescue medication
- Any therapeutic EGD (defined as dilatation or other intervention for a narrowing or stricture of the esophagus) at any point during the study through Week 24.

Further clarification and handling of ICE including prohibited/rescue medications is detailed in [Appendix 2](#).

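### SAP 6.11.5 misstates which bi-weekly DSQ scores to blank: read literally, the MNAR analyses leave dropouts' Weeks 23–24 MAR draws in place, although the surrounding text intends the opposite

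*SAP*

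**What the plan says.** SAP 5.4.2 handles post-ICE diaries first: "The PRO daily scores will be set to missing if they are collected after subjects have experienced an ICE". Bi-weekly scores are formed from the remaining days. Missing bi-weekly scores, through Weeks 23–24, are then imputed 50 times within each treatment group, and the sample code fills every gap ("mcmc chain=multiple impute=full initial=em nbiter=200 niter=100").

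SAP 6.11.5 describes the placebo-based and tipping-point analyses as "constructed based on the already imputed bi-weekly data set from Section 5.4.2". From that data set, "the bi-weekly DSQ is set to missing if it is derived from the daily scores collected on/after ICE event". The section continues: "This setting creates the monotone missing data set". Both sample programs use `monotone reg`.

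The first ICE listed in SAP 4.2.4 is "Premature discontinuation from the study". Other ICE subjects stay in follow-up. Of rescue users, Protocol 8.1 says: "Subjects receiving rescue therapy should remain blinded, continue to receive study drug, and continue to comply with all study visits and assessments".

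**The concern.** The two sections do not fit together. By the time 6.11.5 begins, a score for an interval after the ICE is a within-arm MCMC draw and has no diaries behind it. A rule that selects scores by the diaries they came from therefore passes over the scores that the MNAR analyses are meant to challenge.

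This holds for both kinds of ICE subject. Those who leave the study never had later diaries. Those who stay, such as rescue users, had theirs removed in 5.4.2.

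If the sentence were programmed as it stands, the placebo-based analysis would largely repeat the MAR result. The tipping-point shifts would act on almost no Weeks 23–24 values. The reported robustness of a co-primary endpoint would then say little about missing data.

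**Working it through.** **1. The plan's own figures.** Inputs from SAP 3.6: reductions of 15 and 7.5 (difference 7.5), SD 15, 90% power, 14% dropout. SAP 5.8 gives two-sided 0.05.
- Normal approximation: n = 2 × (1.96 + 1.2816)² × (15/7.5)² = 84.1, so 85 per arm.
- Two-sample t-test: 85.03, so 86 per arm (power at 86 is 90.3%).
- Inflation: 86/0.86 = 100 per arm.

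The stated 86 and 100 reproduce.

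**2. Tracing the rule.** There are 12 bi-weekly intervals, the last being Weeks 23–24. Take an ICE in interval 7, with a diary completed that day.

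| Stage | Intervals 1–6 | Interval 7 | Intervals 8–11 | Interval 12 |
|---|---|---|---|---|
| After 5.4.2 | observed | score from days up to the ICE | MAR draw | MAR draw |
| 6.11.5, literal | observed | blank | MAR draw | MAR draw |
| Every interval from the ICE blanked | observed | blank | blank | blank |

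- Interval 7 is caught only because 5.4.2 removes scores collected after the ICE while 6.11.5 says on or after it. The ICE-day diary survives the first step.
- With no ICE-day diary, the literal rule blanks nothing and the record stays complete.
- The literal row has an interior gap followed by filled values. That is not monotone and does not suit `monotone reg`. The last row is monotone.
- If the ICE falls in Weeks 23–24, the literal rule can blank the endpoint interval.
- Scores missing for reasons other than an ICE stay MAR draws on either reading.

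**3. Size on the planning inputs.** Take 100 per arm, so SE = 15 × √(2/100) = 2.12. Let d be the share of the active arm with an ICE. It is assumed equal to the 14% dropout allowance, with a range of 5–20%, because the documents give no ICE rate. Also assume that placebo-based imputation removes the whole effect in those subjects and that the SE is unchanged.

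- Literal rule: the estimate stays near 7.5 (7.5/2.12 = 3.54, p about 0.0004) at almost any shift.
- Rule as intended: estimate = 7.5 × (1 − d).
- A shift s applied to active ICE subjects only moves the difference by d × s. The tipping shift is (7.5 − 1.96 × 2.12)/d = 3.34/d.

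| d | Placebo-based estimate | p | Active-only tipping shift (DSQ points) |
|---|---|---|---|
| 5% | 7.12 | 0.0008 | 67 |
| 14% | 6.45 | 0.002 | 24 |
| 20% | 6.00 | 0.005 | 17 |

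**4. Where the reading could matter.** Take a hypothetical observed difference of 4.5 and the same SE. The literal rule gives p = 0.034. The intended rule at 14% gives 4.5 × 0.86 = 3.87 and p about 0.068.

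**The case against.** The strongest reply is that nobody reading the whole section would apply the sentence literally.

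- The next sentence claims a monotone data set. For an ICE before the last interval, only blanking from the ICE onward gives a monotone pattern with something left to impute.
- The placebo-based model assumes that active subjects behave like placebo subjects after the ICE. Protocol 15.7.1 says the same, with no restriction to scores that have diaries behind them.
- The note to 6.11.5 calibrates the largest shift on subjects who drop out, the group that the literal rule misses.
- The titles of Tables 14.2.2.2 and 14.2.2.3 in SAP Appendix 3 say that scores due to an ICE are replaced or imputed.

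A literal program would also give a nearly flat plot of p-values against shift (Figure 14.2.2), which might expose the mistake. Neither analysis is in the testing hierarchy of SAP 5.8.

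All of this stands as evidence of intent. A reader might infer that the sensitivity analyses are inert by design, or that the second co-primary endpoint will look robust by construction. The documents do not support that: it follows only if the sentence is programmed against the text around it.

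Evident intent does not repair the rule. SAP section 1 says that the SAP supersedes the protocol's statistical methods. Section 7 outsources programming and relies on independent reprogramming. Two programmers who follow the same sentence can agree on the wrong data set.

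**Conclusion.** The blanking rule is wrong as written, and it is more than a missing detail. It selects at most the interval holding the ICE day, normally leaves dropouts' Weeks 23–24 MAR draws untouched, and does not produce the pattern that the SAP claims and its code needs. The fault is one of specification in two supportive analyses. The primary estimate, power and Type I error are unaffected.

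The gap between the two readings is about 7.5 against 6.45 at an assumed 14% with an ICE, and the estimate as intended runs from 7.1 to 6.0 over 5–20%. These figures assume full loss of effect in active ICE subjects. The drop would be smaller if the pre-ICE trajectory carries over into the imputed values. At the planned effect both readings support the same conclusion. They could part company only for a smaller observed difference, such as the hypothetical 4.5.

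**What to change.** Replace the blanking sentence in SAP 6.11.5 with a rule based on date, for example:

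> For each subject with an ICE, the bi-weekly DSQ for the interval containing the ICE date and for every later interval through Weeks 23–24 is set to missing, whether observed or imputed in 5.4.2 and whether or not diaries exist. Imputations from 5.4.2 are kept only for gaps before the ICE and for subjects without an ICE.

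Three details should go with it:
- Use one ICE date in both 5.4.2 and 6.11.5.
- State that date for the ICEs that SAP Appendix 2 defines by duration. For example, a PPI started after screening and continued to at least Week 21 could be dated from initiation or from Week 21.
- Align the wording of the two sections on whether the ICE day itself is included.

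The cost is one SAP sentence with these clarifications and the matching program step, made before unblinding. The sensitivity results will be somewhat less favourable than under a literal program.
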